11.4 Sample Size Considerations

The selection of 15 patients for this pilot trial is to provide preliminary information for feasibility and safety, as well as to have at least 10 patients with full immune measures pre and post treatment for hypothesis generation and testing in the next trial. An accrual rate of 2 patients per month is anticipated. A maximum sample size of 15 patients will be enrolled. No hypotheses will be formally tested, but with 15 patients we can determine whether an unreasonable proportion of patients have high grade toxicities and gather estimates of immune and molecular changes in tumor and peripheral blood. These measures will be used to design a larger, hypothesis-driven trial.

11.5 Interim Analysis: Safety Monitoring

Any patient who received the first dose of study medication will be included in the ongoing safety monitoring. For trial monitoring and decisions about future trials, a patient will be determined to have an extreme toxicity (ETOX) if either condition is met:

- The patient experiences any grade 3 or higher adverse event (AE) that is possibly, probably, or definitely related to therapy received on this protocol and occurs up to 90 days after the last dose of therapy (durvalumab + tremelimumab). As an exception, any such AE that is potentially treatable with steroids will only count as an ETOX if it does not improve to grade 1 or better within 2 weeks.
- The patient has a delay in surgery of 6 weeks or more due to AE, even if that AE does not meet the definition of ETOX.

Based on the method of Thall (1995)⁹, we will monitor ETOX **continually after the 5th patient** receives treatment. Continuous monitoring will occur monthly. We assume $\Theta_T \sim \text{beta}(0.20, 0.8)$ for the current study, where Θ_T is the probability of a patient experiencing an ETOX. Our stopping rule is given by the following probability statement: $P_T(\Theta_T > 0.20 \mid \text{data}) > 0.90$. That is, we will stop the trial if, at any time during the study, we determine that there is more than a 90% chance that the ETOX rate is more than 20%.

The stopping boundaries for this toxicity rule are to terminate the trial if the number of patients with ETOX compared to the number of patients on trial exceed the limits in table 1, with

operating characteristics for this rule in table 2. After 5 patients, this table will be consulted prior to enrolling each patient. Enrollment will not require waiting for complete information for the previous patient, unless an ETOX in that patient would result in hitting the stopping rule. Boundaries and operating characteristics were calculated in Multic Lean v2.1.

Table 1. Stopping Criteria for Excessive Toxicities Based on ETOX

If there are this many patients with ETOX	3	4	5	6 or more
Stop if this many patients (or fewer) have been evaluated at least once for toxicity	6	10	13	15*

* The trial will stop at 15 patients, but if 6 or more patients experience ETOX, this regimen will be too toxic for further study in this population.

Table 2. Operating Characteristics for Toxicity Monitoring

True ETOX rate	Probability of Stopping Early	Median (25 th %ile, 75 th %ile)	Average Number of Patients	Average Number of Patients with ETOX
0.05	0.003	15 (15, 15)	15.0	0.75
0.10	0.02	15 (15, 15)	14.8	1.5
0.20	0.17	15 (15, 15)	13.7	2.7
0.30	0.45	15 (6, 15)	11.6	3.5
0.40	0.72	8 (5, 15)	9.3	3.7

The Investigator is responsible for completing the summary report and submitting it to the IND Office Medical Monitor for review and approval. A Feasibility/Safety summary will be submitted after the first 5 evaluable patients complete study treatment, and monthly thereafter.

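### Table 1 is first consulted after 5 patients, so 3 ETOX in the first 3 or 4 patients does not trigger it, although a stop at patient 5 is then certain

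*Combined protocol and SAP*

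**What the plan says.** Sections 3.3 and 11.5 give the same rule. The ETOX rate has a beta(0.20, 0.8) prior, and the trial stops when the posterior probability that the rate exceeds 0.20 is above 0.90. Three statements bear on when the rule starts:

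- Monitoring runs "continually after the 5th patient" has received treatment, and for the table, "After 5 patients, this table will be consulted prior to enrolling each patient".
- The criterion is explained as: "we will stop the trial if, at any time during the study, we determine" that it has been met.
- Table 1 is labelled "Stop if this many patients (or fewer) have been evaluated at least once for toxicity". The limits are 6, 10, 13 and 15 patients for 3, 4, 5 and 6 or more ETOX.

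A further clause governs pauses: "Enrollment will not require waiting for complete information for the previous patient, unless an ETOX in that patient would result in hitting the stopping rule". Section 11.5 also asks for a first feasibility and safety summary once 5 evaluable patients have completed treatment. Neither section gives a rule based on the ETOX count for the patients before that.

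**The concern.** Read alone, the first column of Table 1 stops the trial at 3 ETOX in 3 or in 4 patients, since both are 6 or fewer. The posterior criterion does the same. Under the start-up wording nobody consults the table at those points, and enrolment continues to patient 5, where the stop is already settled. A minimum cohort is normally justified because it guards against stopping on a chance cluster of early events. For 3/3 and 3/4 it cannot do so, because no later result can reverse the outcome. The patients concerned have stage II-III disease without known metastases, and section 11.6 says it is not known whether the combination can be used safely before surgery.

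**Working it through.** **Inputs (sections 3.3, 11.4, 11.5).** Prior beta(0.20, 0.8); stop if P(rate > 0.20 | data) > 0.90; Table 1 limits 3/6, 4/10, 5/13, 6/15; maximum 15 patients; accrual 2 per month.

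**1. Reproducing the plan.** With x ETOX in n patients the posterior is beta(0.2 + x, 0.8 + n − x). An exact recursion over (n, x), with looks after every patient from 5 to 14 and reaching 15 not counted as early, gives:

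| True rate | P(stop early), computed / Table 2 | Mean N, computed / Table 2 |
|---|---|---|
| 0.05 | 0.0028 / 0.003 | 14.98 / 15.0 |
| 0.10 | 0.0239 / 0.02 | 14.81 / 14.8 |
| 0.20 | 0.1743 / 0.17 | 13.69 / 13.7 |
| 0.30 | 0.4492 / 0.45 | 11.60 / 11.6 |
| 0.40 | 0.7244 / 0.72 | 9.25 / 9.3 |

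A first look at 6 gives mean N of 11.77 and 9.57 at 30% and 40%. Using Table 1 from the start gives 11.49 and 9.01. Only a first look at 5 matches Table 2 throughout, so the delay is the design that was evaluated.

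**2. Posterior at the early points.**

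| ETOX / patients | P(rate > 0.20) | Formula | Table 1, if consulted |
|---|---|---|---|
| 2/2 | 0.979 | stop | continue |
| 2/3 | 0.932 | stop | continue |
| 3/3 | 0.996 | stop | stop |
| 2/4 | 0.869 | continue | continue |
| 3/4 | 0.983 | stop | stop |
| 2/5 | 0.797 | continue | continue |
| 3/5 | 0.960 | stop | stop |

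Formula and table agree from patient 4 onward and disagree only at 2/2 and 2/3.

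**3. Certainty of the stop.** Three ETOX among the first 4 patients means at least 3 among 5, which is a stop at the first look.

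**4. How often, and how many patients.** With true rate p, P(3/3) = p³ and P(3 or more in 4) = 4p³(1 − p) + p⁴. A trial at 3/3 would save 2 patients, and one first reaching 3 at patient 4 would save 1. The expected saving is therefore P(3/3) + P(3 or more in 4).

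| p | P(3/3) | P(3 or more in 4) | Expected saving |
|---|---|---|---|
| 0.20 | 0.008 | 0.0272 | 0.035 |
| 0.30 | 0.027 | 0.0837 | 0.111 |
| 0.40 | 0.064 | 0.1792 | 0.243 |

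**5. Operating characteristics under each change.**

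- Table 1 acted on as soon as 3 ETOX are seen: P(stop early) is identical to four decimals at every rate. Mean N is 13.65, 11.49 and 9.01 at 20%, 30% and 40%. Mean ETOX at 30% and 40% is 3.45 and 3.60, against 3.48 and 3.70 now.
- First look at patient 4, by table or formula: P(stop early) is again identical. Mean N is 13.66, 11.52 and 9.07; mean ETOX at 30% and 40% is 3.46 and 3.63.
- Formula applied literally from the start: P(stop early) rises from 0.024 to 0.042 at 10% and from 0.174 to 0.212 at 20%, because 2/2 and 2/3 now stop the trial.

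**6. Delay in outcomes.** Step 4 assumes each outcome is known before the next patient is treated. The ETOX window runs to 90 days after a second dose given at about day 28, so to about day 118, while a patient arrives roughly every 15 days. A steroid-treatable event counts only if it has not improved to grade 1 or better within 2 weeks. The documents give no onset times, so I assumed onset uniform from first dose, a 30% rate and one patient every 15.2 days. Among simulated trials with 3 or more ETOX in the first 4, the share with 3 known before patient 5 is treated is then:

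| Onset spread over | No lag | 14-day lag |
|---|---|---|
| 118 days | 3% | 0.5% |
| 56 days | 27% | 5% |
| 28 days | 69% | 21% |

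**The case against.** The start after patient 5 is disclosed in the same paragraph as the rule, and Table 2 was computed on it. The phrase about stopping at any time can fairly be read as any look from then on. That weakens the charge of contradiction in the prose, but the (or fewer) label in Table 1 still covers 3/3 and 3/4 without qualification.

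A reader might infer that the run-in buys nothing at all. The documents do not support that: it is what keeps the formula from stopping the trial at 2/2 and 2/3, where a later stop is not certain and the false-stop probability would rise. Only 3/3 and 3/4 go unprotected for no return.

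A reader might also infer that the text forbids acting before patient 5. It does not. It says when the table is consulted and does not bar an earlier pause. Under section 10.1.2, serious events go to the IND Office within 5 working days, and unexpected related life-threatening or fatal events within 24 hours. Those channels stand, but they are not a rule on the ETOX count.

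The delay in outcomes also stands. Patients 4 and 5 may already be on treatment before three ETOX are established, so the savings in step 4 are upper limits.

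**Conclusion.** The point holds for two outcomes only: 3 ETOX in the first 3 patients, or 3 in the first 4. There the printed Table 1 column and the criterion both indicate a stop, the stop at patient 5 is certain, and waiting improves no stopping probability. An affected trial may treat 1 or 2 more patients. Averaged over all trials this is at most 0.04, 0.11 and 0.24 patients at true rates of 20%, 30% and 40%, assuming immediate and independent outcomes; with realistic delay it is less. This is a minor clarification of the safety rule. It does not call the boundary or the stopping probabilities in Table 2 into question.

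**What to change.** In sections 3.3 and 11.5, state that:

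- Table 1 is the operative boundary and is consulted before each enrolment as soon as 3 ETOX have been observed, including before patient 5.
- The posterior criterion, as a formula, applies from the fifth patient, so 2/2 and 2/3 do not stop the trial.
- The sentence about stopping at any time is subject to these two start points.

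Starting the table earlier without the second statement would leave formula and table in conflict at 2/3. A simpler alternative is a first look at patient 4, where the two agree; it gives up only the second patient saved at 3/3.

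The cost is wording in two sections and a few cells of Table 2. Under the Table 1 option, mean N at 30% and 40% becomes 11.5 and 9.0, and mean ETOX 3.4 and 3.6. With a first look at 4, mean N becomes 11.5 and 9.1, and mean ETOX 3.5 and 3.6. Table 1 and the stopping probabilities stay as printed. The text should also say whether the waiting clause applies from the new start. If it does, enrolment could pause once 2 ETOX are seen among the first 2 or 3 patients. P(2 or more in 3) = 3p²(1 − p) + p³, which is 2.8% at a true rate of 10% and 10.4% at 20%.

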3.2 Study schema

Figure 1. Study Schema

Notes:

- A. Eligible patients include those with HR+/HER2- breast cancer, clinical stage II-III, planned for neoadjuvant chemotherapy.
- B. The first day of dosing is considered Day 1. Tremelimumab will be administered first. The duration of tremelimumab infusion will be 1 hour. Durvalumab infusion will start approximately 1 hour after the end of the tremelimumab infusion. The duration of durvalumab infusion will be 1 hour.
- C. Neoadjuvant systemic therapy will begin within 28 days of the last infusion of tremelimumab and durvalumab.
- D. Surgery will be performed within 8 weeks of completing neoadjuvant systemic therapy.

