3.3 Study Oversight for Safety Evaluation

The study would be stopped if an unacceptable number of patients experience an extreme toxicity (ETOX). For trial monitoring, a patient will be determined to have an ETOX if either condition is met:

- The patient experiences any grade 3 or higher adverse event (AE) that is possibly, probably, or definitely related to therapy (durvalumab + tremelimumab) received on this protocol and occurs up to 90 days after the last dose of therapy. As an exception, any such AE that is potentially treatable with steroids will only count as an ETOX if it does not improve to grade 1 or better within 2 weeks.

- The patient has a delay in initiation of neoadjuvant systemic therapy of 6 weeks or more due to AE, even if that AE does not meet the definition of ETOX.

Based on the method of Thall (Thall et al 1995), we will monitor ETOX continually after the 5th patient receives treatment. We assume $\Theta_T \sim \text{beta}(0.20, 0.8)$ for the current study, where Θ_T is the probability of a patient experiencing an ETOX. Our stopping rule is given by the following probability statement: $P_T(\Theta_T > 0.20 \mid \text{data}) > 0.90$. That is, we will stop the trial if, at any time during the study, we determine that there is more than a 90% chance that the ETOX rate is more than 20%.

The stopping boundaries for this toxicity rule are to terminate the trial if the number of patients with ETOX compared to the number of patients on trial exceed the limits in table 1, with operating characteristics for this rule in table 2. After 5 patients, this table will be consulted prior to enrolling each patient. Enrollment will not require waiting for complete information for the previous patient, unless an ETOX in that patient would result in hitting the stopping rule.

Table 1. Stopping Criteria for Excessive Toxicities Based on ETOX

If there are this many patients with ETOX	3	4	5	6 or more
Stop if this many patients (or fewer) have been evaluated at least once for toxicity	6	10	13	15*

* The trial will stop at 15 patients, but if 6 or more patients experience ETOX, this regimen will be too toxic for further study in this population.

Table 2. Operating Characteristics for Toxicity Monitoring

True ETOX rate	Probability of Stopping Early	Median (25 th %ile, 75 th %ile)	Average Number of Patients	Average Number of Patients with ETOX
0.05	0.003	15 (15, 15)	15.0	0.75
0.10	0.02	15 (15, 15)	14.8	1.5
0.20	0.17	15 (15, 15)	13.7	2.7

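### Table 2 assumes each patient's ETOX status is known before the next enrolment, which the plan does not say; under the written rule, early stopping is less likely if ETOX appears late

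*Combined protocol and SAP*

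**What the plan says.** Sections 3.3 and 11.5 stop the trial when the posterior probability that the ETOX rate exceeds 0.20 is above 0.90, with a beta(0.20, 0.8) prior. Table 1 gives the boundaries. Table 2 is offered as the operating characteristics of this rule, and 11.5 names only the software used. At a true rate of 0.40, Table 2 gives a 0.72 chance of stopping early and 9.3 patients on average.

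Five features decide how the rule works in practice:

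- **Waiting.** "Enrollment will not require waiting for complete information for the previous patient", "unless an ETOX in that patient would result in hitting the stopping rule".
- **Denominator.** The text above Table 1 uses the number of ETOX "compared to the number of patients on trial exceed the limits in table 1". The table row reads "Stop if this many patients (or fewer) have been evaluated at least once for toxicity".
- **Window.** A related grade 3 or higher event counts if it "occurs up to 90 days after the last dose of therapy". Events that may respond to steroids need up to two more weeks to classify.
- **Look schedule.** Both sections consult the table before each enrolment after 5 patients. Section 11.5 also says that the continuous monitoring is done monthly.
- **Second ETOX condition.** In 3.3: "The patient has a delay in initiation of neoadjuvant systemic therapy of 6 weeks or more due to AE". In 11.5 and the synopsis: "The patient has a delay in surgery of 6 weeks or more due to AE".

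**The concern.** Table 1 is the patients' protection against an over-toxic regimen, and Table 2 tells the reader how well it works. Table 2 has no allowance for statuses that are still open. In the written rule a patient can enter the denominator at the first toxicity review (scheduled for Cycle 2 Day 1, about day 28) while an ETOX can still occur about 90 days later. Until it does, that patient counts as ETOX-free. The hold looks only at the previous patient, so several other open statuses can sit behind a decision to enrol. If ETOX tends to come late, the trial stops less often, or later, than Table 2 says. More patients are then treated with a regimen that the rule is meant to stop.

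**Working it through.** **Inputs.** Maximum 15 patients and 2 patients per month (11.4); prior, cut-off, Table 1 and Table 2 (11.5); two doses four weeks apart (3.1); 90-day window after the last dose (3.3, 11.5). Time from first dose to ETOX is not in the documents and is assumed below.

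**Step 1: Table 1.** With x ETOX in n patients the posterior is beta(0.20 + x, 0.80 + n - x). P(rate > 0.20) is:

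- 3 of 6: 0.928; 3 of 7: 0.886
- 4 of 10: 0.904; 4 of 11: 0.869
- 5 of 13: 0.920; 5 of 14: 0.893
- 6 of 15: 0.951

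The 0.90 cut-off gives exactly the printed boundaries.

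**Step 2: Table 2 with every status known.** This is an exact binomial recursion, one patient at a time, with looks at n = 5 to 14.

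| True rate | P(stop), stated | P(stop), recomputed | Mean N, stated | Mean N, recomputed |
|---|---|---|---|---|
| 0.05 | 0.003 | 0.0028 | 15.0 | 14.98 |
| 0.10 | 0.02 | 0.0239 | 14.8 | 14.81 |
| 0.20 | 0.17 | 0.1743 | 13.7 | 13.69 |
| 0.30 | 0.45 | 0.4492 | 11.6 | 11.60 |
| 0.40 | 0.72 | 0.7244 | 9.3 | 9.25 |

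All rows agree, so Table 2 is a known-status calculation.

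**Step 3: how many statuses are open.** Window from first dose: 28 + 90 = 118 days. Spacing at 2 per month: 15.2 days. 118 / 15.2 = 7.8, so with even spacing at most 7 earlier patients are pending at an enrolment. The average over the looks is about 5-6.

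**Step 4: the written rule, simulated.** With n patients enrolled and K known ETOX: stop if K reaches Table 1; hold if the previous patient is still open and K + 1 would reach Table 1; otherwise enrol. Assumptions for the main figures: Poisson accrual that pauses during a hold, first evaluation at day 28, Table 1 applied continuously after the 5th patient, onset uniform over the interval shown. The other-settings column uses enrolled patients as the denominator and/or evenly spaced accrual. True rate 0.40:

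| Onset, days from dose 1 | P(stop before 15th enrolment), 2/month | Other settings, 2/month | Mean treated, 2/month | P(stop), 1.25/month |
|---|---|---|---|---|
| Table 2 | 0.72 | - | 9.3 | - |
| 0-28 | 0.73 | 0.70-0.73 | 9.3 | 0.73 |
| 0-56 | 0.70 | 0.68-0.72 | 9.8 | 0.72 |
| 0-118 | 0.58 | 0.54-0.61 | 11.3 | 0.66 |
| 28-118 | 0.50 | 0.48-0.54 | 12.0 | 0.63 |
| 56-118 | 0.42 | 0.39-0.43 | 12.7 | 0.59 |

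The rate 1.25 per month is 15 patients in 12 months.

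- At a true rate of 0.30 (stated 0.45), 2 per month gives 0.32 for onset 0-118 and 0.27 for 28-118.
- Adding 14 days for the steroid exception gives 0.50 and 0.42 at 0.40 for the same two intervals.
- Monthly looks, with evenly spaced accrual, give 0.54, 0.44 and 0.33 for 0-118, 28-118 and 56-118, against 0.57, 0.52 and 0.43 with a look before each enrolment.

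**Step 5: a hold on all pending patients.** If enrolment waits whenever ETOX in the pending patients together could reach the boundary, P(stop) at 0.40 is 0.71-0.74 for every onset run, which is Table 2 within simulation error. The cost is time. Among trials not stopped (onset 0-118, 2 per month, accrual pausing during a hold), 15 patients enrol within 12 months in about 36%, 23% and 10% of trials at true rates 0.05, 0.10 and 0.20. With the previous-patient hold the figures are about 94-99%. These times run from first enrolment. The criterion in 11.3.1 runs from first screening, so they are slightly optimistic.

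**The case against.** The strongest reply is that the size of the loss is wholly assumed. The documents give no onset times, and if ETOX appears within about 8 weeks Table 2 is close to right. This stands: the undisclosed assumption is established, the magnitude is not. A reader might take 0.5-0.6 as the true stopping probability, but that is only the middle of a range from about 0.4 to 0.7.

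A second reply is that the waiting sentence has an exception. This also stands. Read without it, the sentence suggests enrolment with no hold at all, which would lower the figures much further (0.39 for onset 0-118). The documents do not support that reading. If the exception was meant to cover all pending patients, Table 2 is right as printed, but the text says only that one patient.

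Third, this is a 15-patient pilot with no formal test. Serious events go to the IND Office within 5 working days (10.1.2), a summary goes to the Medical Monitor monthly (11.5), and 6 or more ETOX lead to a conclusion of too toxic (11.6). Counting boundary crossings after the 15th enrolment raises the total to 0.69 (onset 0-118) and 0.67 (28-118). These points limit the consequence. They do not make Table 2 describe the written rule, and late crossings come after all 15 patients have started treatment.

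A reader might also infer that the surgery-delay condition makes monitoring unworkable. The documents do not support a figure for this. They give no length for neoadjuvant chemotherapy, and 8.1.3 allows surgery directly after the two doses.

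**Conclusion.** The point holds. Table 2 reproduces only with each status known before the next enrolment, and the plan does not say so. Confidence in this is high.

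Confidence in the size is moderate. At a true rate of 0.40, 2 patients per month and the previous-patient hold, 0.72 becomes about 0.7 for onset within 8 weeks, 0.55-0.6 over days 0-118, about 0.5 over days 28-118 and about 0.4 over days 56-118. Mean patients treated is 9.3 to 12.7 against 9.3 stated, so up to 12.7 - 9.3 = 3.4 more. At 1.25 per month the range is about 0.6 to 0.73. These are scenarios, not bounds.

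It would be wrong to conclude that the boundaries are faulty or that Table 2 contains an arithmetic error. Both are correct for the calculation they represent. The conflict over the second ETOX condition is a separate contradiction, which bears on this point because it changes when a status is settled. This should be fixed, because safety is a primary endpoint and readers judge the protection from Table 2.

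**What to change.** 1. In 3.3 and 11.5, state whether the hold covers only the previous patient or all pending patients. Use one denominator in the text and Table 1, say how patients with an open window count, and reconcile monthly monitoring with consulting the table before each enrolment.
2. Replace Table 2 with operating characteristics simulated for that rule over stated onset ranges (for example 0-28, 0-56, 0-118 and 28-118 days) and accrual ranges (for example 1.25-2 per month). At the least, label Table 2 as assuming that status is known at each look, and add delayed-onset rows.
3. Before re-simulating, reconcile the second ETOX condition between 3.3 and 11.5 with the synopsis, and state when its status counts as settled.
4. If the hold covers all pending patients, report the expected enrolment time against the 12-month feasibility criterion, with the assumption about candidates who arrive during a hold.

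The Table 1 boundaries and the sample size need no change. The cost is a short simulation and a few sentences. The downside is less favourable stated operating characteristics if the narrow hold is kept, or slower enrolment if the wider one is chosen.
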